8.5 Risk-to-Benefit Rationale

The Nucleus 7 sound processor Clinical Evaluation Report (CER) [10] states that all hazards associated with the Nucleus Smart App have been classified as having "Low" or "Medium" residual risk of harm. The CER concludes that the clinical safety (risks) and performance benefit of devices relevant to anticipated performance of the Nucleus 7 sound processor including the Remote Assist

functionality on iOS devices have been evaluated, and the data demonstrate that the device has a favourable safety profile and is effective. The Cochlear-Sponsored clinical investigations and systematic literature review, coupled with the design verification/validation and post-market surveillance data, establish that the benefits of the device outweigh the risks.

Participants will only use the IMD only during the study sessions and will be asked to use their own devices at other times.

The Remote Assist system Hazards Analysis report [4] concludes that the overall risks for RA fall within the low and medium regions of risk acceptability. The post market surveillance monitoring will continue throughout the lifecycle of Remote Assist in accordance with the Product Risk Management Procedure [1]. Any new or increased risks will be managed in accordance Product Risk Management Procedure [1].

9 STATISTICAL CONSIDERATIONS

9.1 General Considerations

The summary of primary and exploratory outcome measures will be descriptive providing summary statistics reflecting the outcome measures as appropriate. Means, standard deviations, ranges will be reported for continuous variables. Numbers, percentages, and totals will be reported for binary or ordinal variables. Missing data will not be imputed. Demographic and safety data will be summarised descriptively.

Pass / fail criteria: The investigator or observer will rate the participant's ability to complete the primary tasks listed in Table 6 using the rating scale in Figure 3. If the participant is unable to complete the task (rating 1, unable to complete) in the final version of Remote Assist then it will be considered as a fail.

9.2 Outcome measures

9.2.1 Primary Outcome measure

Proportion of subjects who, while using the final version of Remote Assist, are able to complete the primary tasks determined by an observer using a rating scale.

9.2.2 Secondary Outcome measures

There is no secondary outcome measure.

9.2.3 Exploratory Outcome measures

- The median rating on the ability to understand the clinician via the RA video call.
- The median time taken for RA to make changes to the MAP over the internet.

9.3 Hypotheses

No formal testable hypotheses are applicable.

9.3.1 Primary Hypothesis

No formal testable hypotheses are applicable.

9.3.2 Secondary Hypothesis

No formal testable hypotheses are applicable.

9.3.3 Exploratory Hypothesis

No formal testable hypotheses are applicable.

9.4 Sample Size Determination

The primary outcome measure of this study is the proportion of subjects who, while using the final version of Remote Assist, are able to complete the primary tasks.

Observations will be used to determine the participant's ability to complete the tasks. Different versions of the IMD will be used in an adaptive procedure to assess the usability and to make incremental changes in the IMD. This actual use study will be conducted as per summative usability test standards.

A minimum of 15 test participants will be used for this study. As per standard HE75:2009(R2018) Human Factors Engineering – Design of Medical Devices (AAMI HE75, 2018) and Applying Human Factors and Usability Engineering to Medical Devices: Guidance for Industry and Food and Drug Administration Staff (UCM259760, 2016), a minimum of 15 test participants per user group is recommended for summative evaluation testing.

9.5 Analysis Populations

Full analysis set is generally recommended over per protocol set analysis for randomised controlled studies with multiple arms (Ranganathan, Pramesh, & Aggarwal, 2016) As this study does not involve randomisation and any subjects who withdraw will be replaced, per protocol set analysis is appropriate for this study. Primary and exploratory analysis will be completed with per protocol set data. If a participant withdraws after completion of the primary outcome measure but not the exploratory outcome measure, their data will be included in the analysis. Safety analysis will be completed with the full analysis set data to ensure that all safety issues are taken into consideration.

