prior to use in the study. This study aims to continue to gain experience in as many actual use scenarios as possible to account for possible real-world scenarios. There is a possibility that product issues that were not known to date are uncovered during the study, like usability issues or bugs. The study will use an adaptive procedure to allow the use of unplanned product optimisations. If significant issues are identified that require optimisation or correction of the IMD, then further study sessions will be suspended, and the study will resume with the new device iteration. Where optimisation is required to improve usability or performance (see Table 4), subjects will receive a new device iteration. When a new version of RA is issued participants will be asked to attend a study visit to assess the usability of the new iteration (see Figure 2), and they will be asked to re-complete the session at ‘take-home use’ so that the RA can be re-tested outside the clinical environment, and feedback can be received after each take-home period (see Figure 2).

While there are no expected unplanned product changes, early product can be sensitive to the low-risk issues identified in Table 4. Table 4 also identifies how issues will be investigated and retested by the research subjects. All product issues will be recorded as device deficiencies.

[figure not shown]

Figure 2: Flowchart of adaptive procedure

Table 4. Product adaptation categories and product issue examples

Category	Example of a product issue	Action
Connectivity - The App will be communicating	Interruptions due to smart phone notifications (calls, messages, general	If the issue has an impact on performance or usability, the product

Category	Example of a product issue	Action
with the Sound Processor directly via Bluetooth link.	alerts etc.) that affect the app and tests within the app	will be updated and re-evaluated by subjects.
	Data upload issues due to unstable internet connection	If the issue has an impact on performance or usability, the product will be updated and re-evaluated by subjects.
	General connectivity issues between processor and smart phone	If the issue has an impact on performance or usability, the product will be updated and re-evaluated by subjects.

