7.2.6 Criteria for Subject Withdrawal

Subjects can decide to withdraw from the investigation at any time. The Investigator shall ask the reason(s), however the subject is under no obligation to give a reason for wanting to withdraw. The reason for withdrawal should be documented in the subject's source files and the case report form (CRF).

The Investigator or Sponsor may also decide to withdraw a subject from the clinical investigation if it is considered to be in the subject's best interests.

Subject withdrawal may be for any of the following reasons:

- Adverse Event (AE)
- Device Deficiency (DD)
- CIP or GCP deviation
- Subject withdrew consent
- Subject lost to follow-up
- Subject death
- Sponsor decision
- Investigator decision
- Other (specify)

If subject withdrawal is due to problems related to the IMD safety or performance, the Investigator shall ask for the subject's permission to continue in safety follow up (i.e., adverse events) until their scheduled End-of-Study visit.

If a subject is lost to follow-up, every possible effort must be made by the study site personnel to contact the subject and determine the reason for discontinuation. At least 3 separate attempts taken to contact the subject must be documented.

Participating subjects who are withdrawn/discontinued will be replaced.

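### The primary proportion rests on a per-protocol set for reasons that do not protect it: a subject who leaves the final version for a device-related reason, with tasks unrated and no rating of 1, would apparently be dropped and replaced

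*Combined protocol and SAP*

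**What the plan says.** Section 9.5 assigns the primary and exploratory analyses to a per-protocol set and gives two grounds: "As this study does not involve randomisation and any subjects who withdraw will be replaced, per protocol set analysis is appropriate for this study". It then covers one kind of withdrawal: "If a participant withdraws after completion of the primary outcome measure but not the exploratory outcome measure, their data will be included in the analysis". It is silent on withdrawal before the primary measure is complete and gives no membership rule for the set. The only other statement on membership is in Section 13, which removes data from an investigator or site disqualified for gross misconduct. The full analysis set is used for safety only.

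Section 7.2.6 lists device deficiency and adverse event among the possible reasons for withdrawal and ends with a rule that does not distinguish between reasons: "Participating subjects who are withdrawn/discontinued will be replaced".

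Section 9.1 states "Missing data will not be imputed" and defines a fail only through the lowest score on the scale: "rating 1, unable to complete) in the final version of Remote Assist then it will be considered as a fail". Section 9.6 describes the resulting proportion, and Section 9.3 states that there is no hypothesis.

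**The concern.** The two grounds in Section 9.5 do not support the choice. Lack of randomisation removes the argument about preserving comparability between arms. It does not remove the other problem with dropping subjects: if those who leave are the ones for whom the device worked badly, the proportion describes the remainder. Replacement restores the number of subjects, not the lost outcome.

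The loss here can be related to the outcome. Section 11.1.7 counts use errors as device deficiencies, and Section 7.1.1 records all product issues as device deficiencies, so one listed reason for withdrawal overlaps with what the primary measure is meant to capture. Table 6 has 14 primary tasks, including resuming after processor and internet disconnection, so a subject can leave with some tasks unrated.

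At stake is the meaning of the study's one primary figure. With 15 subjects, a single person separates a report that everybody completed the tasks from a report that somebody did not.

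**Working it through.** **Inputs.** Planned number 15 (Sections 7.2.3 and 9.4); expected dropout 10% (Section 7.2.3); fail = rating of 1, no imputation (Section 9.1); withdrawn participating subjects replaced (Section 7.2.6). The figure of 15 is a recommended minimum taken from usability guidance, with no alpha, power or effect size, so no formula can reproduce it. The number of subjects who would leave the final version for a device-related reason before rating is complete is not given; call it w and treat it as an assumption. For scale, dropout from all causes is expected to be 0.10 × 15 = 1.5 subjects.

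**Step 1: what happens to such a subject.**
- Rated 1 on a task before leaving: meets the fail criterion in Section 9.1, although Section 9.5 does not say that the subject stays in the set after withdrawing.
- All tasks rated, then leaves: kept under Section 9.5.
- Leaves with tasks unrated and no rating of 1: not a fail under Section 9.1, not imputed, not covered by the retention sentence in Section 9.5, and replaced under Section 7.2.6. The combined reading is exclusion. This third group is the whole of the point.

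**Step 2: direction.** Let s of the 15 rated subjects (replacements included) pass.
- Planned proportion: s/15.
- Same data with the w subjects counted as not completing: s/(15 + w).

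Since 15 + w > 15, the planned figure is never the lower of the two; they are equal only if s = 0.

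**Step 3: size, with exact (Clopper-Pearson) 95% intervals.**

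| s | w | Planned | Counted as not completing |
|---|---|---|---|
| 15 | 0 | 15/15 = 100% (78.2 to 100) | no change |
| 15 | 1 | 15/15 = 100% (78.2 to 100) | 15/16 = 93.8% (69.8 to 99.8) |
| 14 | 1 | 14/15 = 93.3% (68.1 to 99.8) | 14/16 = 87.5% (61.7 to 98.4) |

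With s = 15 and w = 1 the difference is 100 − 93.75 = 6.25 points.

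**Step 4: if the unobserved outcome could have gone either way.** The range is s/(15 + w) to (s + w)/(15 + w).
- s = 15, w = 1: 15/16 = 93.8% to 16/16 = 100%. The planned 100% is the most favourable value.
- s = 14, w = 1: 14/16 = 87.5% to 15/16 = 93.8%. The planned 93.3% lies 93.75 − 93.33 = 0.42 points below the most favourable value.

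**The case against.** The strongest reply is that the exposed group is very small.

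- Table 1 places the usability evaluation at the study visit only, Section 7.1 confines device use to study sessions, and Section 7.1.1 calls the testing acute. The subject must therefore leave between starting a final-version session and the end of its rating; this is not attrition over six months of exposure.
- A subject stopped in the middle of a task by a device problem fits the label of rating 1, and so is already a fail if the observer scores it that way.
- The adaptive procedure absorbs many device problems: "If significant issues are identified that require optimisation or correction of the IMD, then further study sessions will be suspended". A version that drives a subject out would often not be the final one.
- The events would not be hidden. Section 9.9 summarises device deficiencies and discontinuations due to adverse events.

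All of this stands, and it makes the case rare. It does not close the gap: iterations are capped at five (Table 1), Table 4 leaves general issues to case-by-case judgement, nothing requires a new version after a withdrawal, and no section carries the Section 9.9 events into the primary proportion.

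A reader might also infer more than the documents support:

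- *That the plan expressly excludes device-related withdrawals.* It does not; exclusion follows only from reading Sections 9.5, 7.2.6 and 9.1 together.
- *That upward bias is shown.* The inequality in step 2 holds in any study that drops a subject instead of counting a failure. The subject might have passed, and with s = 14 the planned figure lies inside the range in step 4.
- *That the gap could readily exceed 10 points.* Two such subjects would give 15/17 = 88.2%, but two is more than the 1.5 withdrawals expected from all causes.
- *That every adverse device effect leading to a stop should be a task failure.* Leaving because of, say, an uncomfortable sound is a matter of tolerability and need not say anything about ability to do the tasks.

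**Conclusion.** The point holds as a flaw in a stated analysis choice and its justification. The two reasons in Section 9.5 do not make a per-protocol set appropriate for a single-arm proportion, and the set has no membership rule. The practical effect is confined to final-version subjects who leave for a device-related reason with tasks unrated and no rating of 1. With none, the effect is zero, which is plausible. With one, and all 15 rated subjects passing, 100% is reported where counting that subject as not completing gives 93.8%.

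This rests on the combined reading of the three sections, an assumed count, and the comparison with counting the subject as not completing. There is no test or success threshold, so no error rate is involved, only the estimate. It should be corrected because it is the only primary result and the correction is cheap. Confidence is medium, since the exclusion is inferred and the case may not arise.

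**What to change.** In Sections 9.5 and 9.6:

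1. Make the primary analysis set all subjects with Participated status (Section 7.2.5) who started a session with the final version, including those later replaced. State that anyone already rated 1 on a task remains a fail after withdrawal.
2. Count as not able to complete those who stop before the rating is complete because of a device deficiency or a performance or usability problem with the investigational device.
3. For all other incomplete subjects (adverse device effects not involving task performance, unrelated reasons, no reason given), report the number and show the proportion with them excluded and with them counted as fails.
4. Report the per-protocol result as a sensitivity analysis, with its membership rule written out.
5. List replaced subjects with the version used and the recorded reason.

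The cost is wording in two sections and one listing; no extra subjects are needed. Section 7.2.6 already has the reason for withdrawal documented in the CRF, and Section 11.2 already records the investigator's opinion on the relation of each adverse event to the device. There are two drawbacks. The reported proportion may be slightly lower. Section 7.2.6 also lets a subject decline to give a reason, so some withdrawals cannot be classified; the two-way presentation in item 3 covers those.

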9.6 Primary Outcome measure Analyses

Proportion of subjects who, while using the final version of Remote Assist, are able to complete the primary tasks as per the pass/fail criteria will be described using descriptive statistics.

9.7 Secondary Outcome measure Analyses

Not applicable for this clinical investigation

9.8 Exploratory Outcome measure Analyses

The rating on the ability to understand the clinician via the RA video call will be described using descriptive statistics.

The time taken for RA to make changes to the MAP over the internet will be described using descriptive statistics.

9.9 Safety Analyses

For AE/ADEs and DDs, the percentage of subjects who experienced at least one occurrence of each, will be summarised. Any subjects who discontinued an intervention due to an AE/ADEs, or who experienced a severe or an SAE/SADEs will be summarised separately.

9.10 Interim Analyses

The usability observations and feedback will be analysed on an ongoing basis and these will be used to improve the product. No formal interim analysis is planned for the usability ratings.

10 INFORMED CONSENT PROCESS

The Investigator shall obtain written informed consent from the subject using an approved ICF prior to any clinical investigation-related examination or activity. The rationale of the clinical investigation, as well as the risks and benefits, what participation will involve, and alternatives to participation will be explained to the subject. Ample time will be provided for the subject to enquire about details of the clinical investigation and to decide whether to participate.

All questions about the clinical investigation shall be answered to the satisfaction of the subject or the subject's legally acceptable representative. Subjects shall not be coerced or unduly influenced to participate or to continue to participate in a clinical investigation.

Each subject (or their legally authorised representative) and the person who conducted the informed consent discussion, shall sign and date the Informed Consent Form (ICF). Where required, a witness shall sign and personally date the ICF. A copy of the signed ICF shall be given to the subject. The original signed ICF shall be archived in the Investigator's Site File or subject file at the investigational site.

The subject, or the subject's legally authorised representative, shall be informed in a timely manner if new information becomes available that may be relevant to the subject's willingness to continue participation in the clinical investigation. The communication of this information must be documented as an update to the ICF and re-consent of the subject.

11 ADVERSE EVENTS AND DEVICE DEFICIENCIES

11.1 Definitions

11.1.1 Adverse Event

An adverse event (AE) is any untoward medical occurrence, unintended disease or injury, or untoward clinical signs (including abnormal laboratory findings) in subjects, users, or other persons whether related to the medical device or the procedures required for implant or use.

NOTE 1: This definition includes events related to the medical device or the comparator device.

NOTE 2: This definition includes events related to the procedures involved.

NOTE 3: For users and other persons, this definition is restricted to events related to medical devices.

11.1.2 Adverse Device Effect

An adverse device effect (ADE) is an AE related to the use of a medical device.

NOTE 1: This includes any AE resulting from insufficiencies or inadequacies in the instructions for use, the deployment, the implantation, the installation, the operation, or any malfunction of the medical device.

NOTE 2: This definition includes any event resulting from use error or from intentional misuse of the medical device.

11.1.3 Serious Adverse Event

A serious adverse event (SAE) is any AE that:

- 1) led to a death,
- 2) led to a serious deterioration in the health of the subject that either resulted in:
 - a life-threatening illness or injury, or
 - a permanent impairment of, or damage to, a body structure or a body function, or
 - in-patient hospitalisation or prolonged hospitalisation, or
 - medical or surgical intervention to prevent life-threatening illness or injury or permanent impairment or damage to a body structure or a body function, or
 - Chronic disease.
- 3) led to foetal distress, foetal death or a congenital physical or mental abnormality, or birth defect

NOTE: Planned hospitalisation for a pre-existing condition, or a procedure required by the CIP, without serious deterioration in health, is not considered a SAE.

11.1.4 Serious Adverse Device Effect

A serious adverse device effect (SADE) is an ADE that has resulted in any of the consequences characteristic of a SAE.

11.1.5 Unanticipated Serious Adverse Device Effect

An unanticipated serious adverse device effect (USADE) is a SADE, which by its nature, incidence, severity, or outcome has not been identified in the current version of the hazards analysis [4].

NOTE: An anticipated serious adverse device effect is an effect, which by its nature, incidence, severity, or outcome has been identified in the hazards analysis [4].

11.1.6 Adverse Events of Special Interest

Not applicable for the current clinical investigation.

11.1.7 Device Deficiency

A Device Deficiency (DD) is an inadequacy of a medical device with respect to its identity, quality, durability, reliability, safety, or performance.

NOTE: Device Deficiencies include malfunctions, use errors, and inadequate labelling or information supplied by the manufacturer.

11.2 Recording and Handling of Adverse Events

Subjects shall be carefully monitored during the clinical investigation and the investigator should enquire about AEs at investigation visits.

All AEs will be recorded from the time of first use of the IMD. AE recording will continue for each subject until completion of their End of Study visit. Ongoing SAEs and SADEs will be followed for 30 days, or until resolution or stabilisation of the event, whichever comes first.

Source notes should indicate the evaluation for AEs, even if none to report. All required AEs will be reported if observed, even if anticipated and/or acknowledged as a risk factor in the consent.

All AEs will have the following information documented: start and stop dates, action taken, outcome, severity, and investigators opinion on the potential relationship to the IMD and study procedures. If an AE changes in severity, the most severe (highest) grade will be captured for that event on the Adverse Events CRF.

11.2.1 Assessment of Severity

The Principal Investigator (or qualified delegate) will make an assessment of severity for each event based on clinical judgement. The intensity of each event recorded in the CRF should be assigned to one of the following categories:

Mild	An event that is easily tolerated by the subject, causing minimal discomfort, and not interfering with everyday activities.
Moderate	An event that is sufficiently discomforting to interfere with normal activities
Severe	An event which is incapacitating and prevents normal everyday activities

